3. STUDY OVERVIEW

3.1 Study Design

Subjects in this randomized, double-blind, placebo controlled, parallel-group, multiple-center study will be assigned to treatment with the investigational products or placebo control according to a randomization scheme.

- Part I: 24 weeks: Subjects will be randomized to Placebo,
 or AS012 in 3:3:1:3:1 ratio (approximately first 45% of enrolled subjects) or in 1:1:3:1:3 (approximately remaining 55% enrolled subjects).
- Part II: week 24 to week 52: Subjects initially randomized to placebo will be rerandomized to AS012 in 1:1 ratio. Subjects originally randomized to AS012 doses will remain on their assigned dosing regimen until the end of Part II (week 52).
- Part III: week 52 to week 64: After week 52 (or early termination of study treatment prior to week 52), the study treatment will be stopped, and all subjects will enter the follow-up period to monitor safety and tolerability for 12 weeks following last dose of study treatment.

Clinical Evaluations will be performed at:

- Visit 1: Screening Visit (Week \geq -4 / Day -28 to -1);
- Visit 2: Baseline Visit (Week 1 / Day 1);
- Visit 3: Interim Visit (Week 4 / Day 29 ± 3 Days);
- Visit 4: Interim Visit (Week 12 / Day 85 ± 3 Days);
- Visit 5: Interim Visit (Week 16 / Day 113 ± 3 Days);
- Visit 6: Interim Visit (Week 20 / Day 141 ± 3 Days);
- Visit 7: Interim Visit (Week 24 / Day 169 ± 3 Days);
- Visit 8: Interim Visit (Week 28 / Day 197 ± 3 Days);
- Visit 9: Interim Visit (Week $36 / \text{Day } 253 \pm 3 \text{ Days}$);
- Visit 10: Interim Visit (Week 44 / Day 309 ± 3 Days);
- Visit 11: Interim Visit (Week 48 / Day 337 \pm 3 Days);
- Visit 12: End of Treatment Visit (Week 52 / Day 365 ± 3 Days);
- Visit 13: Follow-up Visit (Week 64 / Day 449 \pm 3 Days);

Subjects will be admitted into the study after informed consent has been obtained. An Unscheduled Visit is allowed at any time, for any reason, if in the Principal Investigator's opinion it is warranted. If a subject is discontinued from the study during an Unscheduled Visit, the Unscheduled Visit will be referred to as an Early Discontinuation Visit. Subjects discontinued from Investigational Product (IP) prior to the end of study will be required to complete the End of Study (EoS) assessment within 2 weeks after the last dose.

Randomization and re-randomization will be stratified by stability of disease (stable vs. non-stable)

The assigned IP will be administered orally three tablets three times a day, in the morning, in the afternoon, and in the evening according to a randomization scheme. Subjects will be required to use diaries to document the date of study treatments, any missed treatments, and the occurrence of all adverse events (AEs).

The duration of each Subject's participation in the study will be approximately 64 weeks (449 days).

If the Principal Investigator determines that the Subject's condition has worsened to the degree that it is unsafe for the Subject to continue in the study (e.g., an increase in VASI score from baseline by $\geq 25\%$), the Subject may be discontinued from the study as a treatment failure and treated using the standard care.

A detailed Schedule of Procedures is provided in Appendix 11.1.

3.2 Sample Size

The study will randomize approximately 320 subjects into 5 treatment arms (n=approximately 64 subjects per arm) in a 1:1:1:1:1 ratio. The sample size assumes a drop-out rate of about 20%, with 52 evaluable subjects per treatment arm at the time of analysis. The study is powered at 85%, and assumes a two-sample Z-test with equal variances, two-sided alpha (α) of 0.05, a Baseline VASI mean of 15.7 and standard deviation of 8.9 and an improvement at Week 24 of 35% (Δ 5.50) for AS012 versus an improvement for placebo of 10% (Δ 1.56), for a mean treatment difference of 3.94. Since the correlation between Baseline and Week 24 VASI scores is expected to be >0.5, the standard deviation of the difference is conservatively estimated at 70% of the Baseline SD, or 6.4. The sample size takes into account an interim assessment of futility and efficacy, using an O'Brien-Fleming error spending function to determine the boundaries, once the placebo, dose reach 75% completion of the Week 24 VASI assessment. Randomization will be stratified by stability of disease (stable vs. non-stable) With a total of six possible stratification levels, 52 evaluable subjects per treatment arm ensures at least 8 subjects per stratification level.

3.3 Randomization and Unblinding Procedures

To maintain the study blind, the randomization schedule will be generated by a third party. Randomization will be performed according to a computer-generated randomization scheme. The placebo and tablets for all strengths of AS012 look alike which ensures blinding. The Investigational Product will be provided in identically labeled and packaged such that neither the Subject nor any Investigator can identify the treatment. The Drug Labeling, Packaging and Shipping facility will hold the randomization code throughout the conduct of the study in order to minimize bias. A sealed copy of the randomization scheme (as a scratch off portion of the product label attached to the drug accountability page) will be retained at the study site. In the event of an emergency, the Subject-specific treatment may be identified; however, every effort should be made to maintain the blind. Where possible, the Medical Monitor should be contacted before breaking the blind for any subject. The Sponsor must be notified in the event the blind is broken.

The treatment assignments will remain blinded until the final database is closed.

If Suspected Unexpected Serious Adverse Reactions (SUSAR) requires unblinding by a Regulatory Agency, a designated member of the Sponsor's safety team will be un-blinded on case-by-case basis by receiving the randomization directly from the study unblinded statistical consultant.

The bioanalytical team will analyze the samples collected from all subjects, including samples from subjects assigned to placebo to ease the selection of samples and avoid releasing the randomization code.

4. STUDY ENDPOINTS/OUTCOMES

4.1.1 Primary endpoint

[figure not shown]
The primary endpoint is change from baseline in VASI score at Week 24.

[figure not shown]
4.2 Key secondary endpoints

Key secondary endpoints of this study are:

- Change from baseline in VES at Week 24.
- Change from baseline in VIPs at Week 24

4.3 Other secondary endpoints

5. ANALYSIS POPULATIONS

5.1 Safety Population

The Safety Population will consist of all subjects who were randomized into the study and dispensed study drug. This population will be the primary population for the safety analysis. Subjects will be analyzed according to the actual treatment received.

5.2 Intent-to-Treat (ITT) Population

The Intent-to-Treat (ITT) Population will consist of all randomized subjects regardless of whether they received the investigational product. This population will be the main population for the efficacy analyses. Subjects will be analyzed according to the treatment they were randomized to receive.

6. STATISTICAL METHODS OF ANALYSIS

6.1 General Principles

The statistical analyses will be performed by Quartesian LLC, with approval of the Sponsor, using SAS Version 9.4 (or higher). All tables, figures and listings will be produced in landscape format.

In general, all data will be listed by subject and visit/time point where appropriate. The summary tables will be stratified by, or have columns corresponding to, treatment groups.

The total number of subjects in the treatment group (N) under the specified population will be displayed in the header of summary tables.

Data will be summarized using descriptive statistics for continuous variables. Unless otherwise specified, descriptive statistics will include number of subjects, mean, standard deviation, minimum, median and maximum. Number of subjects with missing values will also be displayed, but only if non-zero. The minimum and maximum statistics will be presented to the same number of decimal places as the original data. The mean and median will be presented to one more decimal place than the original data. The standard deviation will be presented to two more decimal places than the original data.

In summary tables of categorical variables, counts and percentages will be displayed. The count [n] indicates the actual number of subjects in a particular category, which should always be less

than or equal to the total number of subjects in the respective study group with known (non-missing) category [M]. Percentage will be obtained by: % = n/M*100. Unless otherwise specified, all percentages will be expressed to one decimal place.

All statistical tests will be two-sided at a significance level of $\alpha = 0.05$, unless otherwise indicated.

Baseline will be defined as the last assessment, scheduled or not, prior to the first dose of the study drug, unless otherwise specified.

In by-visit summaries, only data collected on scheduled visits/timepoints will be summarized. Data from unscheduled assessments will be included in listings and may be used in determination of baseline if applicable.

Relative days will be calculated relative to date of first dose of the study drug. Relative days will be calculated as follows only when the full assessment date is known (i.e., partial dates will have missing relative days).

For assessment on or after the day of first dose of the study drug:

Relative Day = Date of Assessment – Date of First Dose of Study Drug+1.

For assessment before the day of first dose of the study drug:

Relative Day = Date of Assessment – Date of First Dose of Study Drug.

All dates will be displayed in DDMMMYYYY format.

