## 5.5 Laboratory Assessments

A central laboratory will be used for all assessments unless noted otherwise. Unscheduled laboratory assessments can be performed at discretion of the investigator in response to AEs. The laboratory assessments include:

Thyroid function\*: at study visits 1, 7 and 12 (screening and weeks 24 and 52) a blood sample will be collected for free T4 and TSH testing.

Hematology\*: at all study visits a blood sample will be collected for total and differential WBC count, Absolute Neutrophil count (ANC), Absolute Lymphocyte count (ALC), Platelet count, Hemoglobin, Hematocrit.

Lipid profile: at the study visits 1, 2, 7, and 12 (Screening and study weeks 1, 24, and 52) a blood sample will be collected for LDL, HDL and total cholesterol and Triglycerides testing. The test does not need to be repeated at study visit 2 if the screening assessment (visit 1) was performed within 2 weeks of visit 2.

Clinical chemistry\*: at all study visits a blood sample will be collected for sodium, potassium, chloride, calcium, magnesium, bicarbonate, phosphate, blood urea nitrogen, random glucose, albumin, total protein, alkaline phosphatase, creatinine, ALT, AST, gamma glutamyltransferase (GGT), total bilirubin, conjugated bilirubin testing.

Coagulation profile\*: at the study visits 1, 2, 7 and 12 (Screening and study weeks 24, and 52) a blood sample will be collected for PT and INR testing. The test does not need to be repeated at study visit 2 if the screening assessment (visit 1) was performed within 2 weeks of visit 2.

Serology: at Screening visit a blood sample will be collected for: HIV antibodies, HBsAg, and HCV antibodies testing.

Serum pregnancy test: at Screening visit a blood sample will be collected for serum beta-hCG testing.

The following tests will be performed at a clinic site:

Urinalysis dipstick: at the study visits from 1 to 12 (Screening and study weeks 1 to 52) a urine sample will be collected for pH, specific gravity, protein, glucose, ketones, and blood testing. The test does not need to be repeated at study visit 2 if the screening assessment (visit 1) was performed within 2 weeks of visit 2.

Microscopic exam may be performed at the local or central laboratory at the discretion of the investigator if the dipstick is positive (i.e. trace or above).

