# 7.15 Unscheduled Visits and Early Discontinuation Visit

An Unscheduled Visit is allowed at any time, for any reason, if in the Principal Investigator's opinion it is warranted. If the Unscheduled Visit is due to an AE, the Principal Investigator will determine whether additional visits are needed.

If a Subject is discontinued from the study during an Unscheduled Visit, the Unscheduled Visit will be referred to as an Early Discontinuation Visit:

- 1. A urine pregnancy test will be conducted for all females of childbearing potential (see Section 5.4)
- 2. The use of concomitant medications since the previous study visit will be documented and assessed. (See Section 5.6)
- 3. The occurrence of all AEs will be assessed and documented following the procedures in Sections 5.7, 10.1, and 10.3

Additional assessments may be performed per the Investigator's decision.

For all the subjects who discontinue the study prior to Visit 7 all efforts should be made to conduct a visit at, or close to week 24 to collect focused area assessments. Regardless of the reason, Subjects discontinued from IP prior to the end of study will be required to complete the End of Study (EoS) assessment within 2 weeks after the last dose.

If the Subject's condition has worsened to the degree that it is unsafe for the Subject to continue in the study, the Subject may be discontinued from the study as treatment failure and a standard of care treatment may be advised at the Principal Investigator's discretion.

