# 10.4 Suspected Unexpected Serious Adverse Reactions (SUSARs)

An Adverse Event or Suspected Adverse Reaction is considered a SUSAR if it is serious, unexpected, and suspected. Prior to reporting to the applicable Regulatory Authorities, the IND Sponsor will evaluate the available evidence and to judge the likelihood that the drug actually caused the adverse event. The SUSAR must be reported to FDA within 15 days, or if fatal or life threatening, within 7 days, by the IND Sponsor. The IND Sponsor must report an adverse event as a suspected adverse reaction only if there is evidence to suggest a causal relationship between the drug and the adverse event. Additionally, potential Hy's law cases will be reported as SUSARs.

The applicable Regulatory Authorities shall be notified by Sponsor Safety Physician of any SUSAR, as per local Regulatory Authorities guidelines and timeframe specified as per local regulation.

May 20, 2022 Protocol: **AS012-20-01** Page 57 of 88

All participating Investigators, IEC/IRB and other stakeholders shall be notified of any SUSAR by CRO's Medical Monitor as per local regulatory requirement.

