A positive result should be confirmed by a different brand of UPT. A confirmed positive urine pregnancy test during the treatment periods of the study requires immediate interruption of study treatment and the subject must be discontinued from the study.

For hematology, chemistry, thyroid function, and coagulation profile the labs that were abnormal and clinically significant at end of treatment (Week 52) are needed at safety follow-up visit (Week 64).

Hematology, chemistry (including lipid profile and thyroid function, and coagulation parameters and their changes from baseline will be summarized descriptively by visit and treatment group. Urinalysis dipstick results will be summarized categorically (positive or negative).

Shifts from baseline among the categories Normal (within the reference range), Low (below the reference range), and High (above the reference range) will be presented by visit.

All results will be listed.

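### Laboratory, vital-sign and ECG values from unscheduled and early discontinuation visits appear only in listings, because the visible SAP tabulates blood tests, vital signs and ECG by scheduled visit and shows no worst-value summary

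*SAP*

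**What the plan says.** SAP 6.1 sets the general rule: "In by-visit summaries, only data collected on scheduled visits/timepoints will be summarized". The next sentence says where the rest goes: "Data from unscheduled assessments will be included in listings and may be used in determination of baseline if applicable".

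The safety sections then use by-visit displays. For hematology, chemistry, lipids, thyroid function and coagulation, SAP 6.11.2 says the parameters and "their changes from baseline will be summarized descriptively by visit and treatment group". For the shift tables it says: "Shifts from baseline among the categories Normal (within the reference range), Low (below the reference range), and High (above the reference range) will be presented", again by visit. SAP 6.11.3 and 6.11.4 use the same by-visit layout for vital signs, ECG intervals and the overall ECG interpretation. The dipstick summary in 6.11.2 is categorical and is not stated to be by visit.

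The protocol describes where off-schedule values come from. Section 5.5: "Unscheduled laboratory assessments can be performed at discretion of the investigator in response to AEs". Section 7.15: "If a Subject is discontinued from the study during an Unscheduled Visit, the Unscheduled Visit will be referred to as an Early Discontinuation Visit". Section 10.4, on expedited reporting, adds: "Additionally, potential Hy's law cases will be reported as SUSARs".

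**The concern.** Unscheduled bloods are, on the protocol's own description, taken because something happened to the subject. A rule that keeps them out of every numeric table removes values for a reason connected with safety. Protocol 9.7 evaluates safety partly through shifts from baseline in laboratory tests and through frequencies of ECG findings, and sets no scheduled-visit limit; the SAP adds that limit. The treatment of off-schedule data is also uneven: before dosing such a value may become the baseline, but after dosing it enters no by-visit summary.

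This is a dose-ranging study. A listing holds the peak value but does not compare arms. If the reader of the report has only scheduled-visit tables and AE counts, the size of an off-schedule abnormality cannot be compared across doses without hand work on the listings.

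**Working it through.** There is no figure in the plan to reproduce, so the check is mainly a reading of the sections together.

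**1. Which tables the 6.1 rule reaches.**

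| Data | SAP section | Layout stated | Unscheduled values included? |
|---|---|---|---|
| Blood tests, values and changes | 6.11.2 | by visit | No |
| Laboratory shifts | 6.11.2 | by visit | No |
| Dipstick | 6.11.2 | categorical, visit not stated | Unclear |
| Vital signs | 6.11.3 | by visit | No |
| ECG intervals and interpretation | 6.11.4 | by visit | No |
| TEAEs | 6.11.1 | by SOC/PT, severity, relationship | Event counted if reported; value not shown |

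**2. A subject followed through the rules.** Suppose ALT is normal at Week 4, an AE prompts a draw at Week 7 with a high ALT, and the subject leaves the study that day. The shift table shows this subject as normal at Week 4 and nothing later. The Week 7 value is listed. The AE is counted as a TEAE and, if it caused the withdrawal, in the table of AEs leading to discontinuation. The EoS assessment is due within 2 weeks of the last dose, but Protocol 7.13 takes bloods there only for tests that were abnormal and clinically significant at Visit 12, a visit this subject never had. The unscheduled draw may therefore be the only laboratory record of the episode.

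**3. Early discontinuers' other data.** Vital signs and ECG are EoS procedures in Protocol 7.13, under the Visit 13 heading. The SAP does not say whether an EoS assessment done early is tabulated as Week 64, at another visit, or only listed.

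**4. Grading.** The shift categories stop at High, so 1.1 × ULN and 10 × ULN fall in the same cell. The by-visit descriptive statistics include the maximum (SAP 6.1), so an extreme value at a scheduled visit would still be seen there; an unscheduled one would not. No visible table sets ALT or AST beside total bilirubin.

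**5. What scheduled draws can miss (illustration).** Input: on-treatment chemistry at Weeks 4, 12, 16, 20, 24, 28, 36, 44, 48 and 52 (visit list in Protocol section 3; chemistry at these visits in sections 7.3 to 7.12). Counting from baseline, this gives seven 4-week gaps and three 8-week gaps: 7 × 4 + 3 × 8 = 52 weeks. Assume uniform onset over 52 weeks, ignore the ±3-day windows, and let an elevation last d weeks. The share containing no scheduled draw is the sum of max(gap − d, 0) over gaps, divided by 52:

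- d = 2: (7 × 2 + 3 × 6)/52 = 32/52 = 62%
- d = 3: (7 × 1 + 3 × 5)/52 = 22/52 = 42%
- d = 4: (7 × 0 + 3 × 4)/52 = 12/52 = 23%

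The durations are assumptions; the documents give none. An elevation for which nobody draws blood is missing under any SAP rule, so these shares describe the schedule, not bias in a table.

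**The case against.** Restricting by-visit tables to scheduled visits is good practice. It avoids uneven ascertainment, since sicker subjects are sampled more often. That stands, and it is why those tables should be kept as they are.

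A reader might infer that off-schedule abnormalities never reach any safety summary. The documents do not support that. Protocol 5.7 counts an abnormal laboratory finding as an AE, and the TEAE tables in SAP 6.11.1 are not tied to visits. A potential Hy's law case reported as a SUSAR should also appear among the serious TEAEs. What is confined to listings is the measured value. AE counts depend on the investigator reporting the finding and carry neither the peak nor its multiple of ULN, so they do not replace a numeric table.

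A reader might also infer that every table is affected, that the excluded values are usually a subject's worst, or that the high-toxicity arm is understated most. The dipstick layout is unstated, and the documents give no data on the other two points. Nor is all early-discontinuation data lost: laboratory tests, ECG and vital signs are optional at the Early Discontinuation Visit (Protocol 7.15), and the required EoS vital signs and ECG may enter as Visit 13. Only unscheduled laboratory draws are described as AE-driven; the protocol does not say this of ECGs.

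Finally, absence from the public text is not proof of absence. The shells are separate (SAP section 9), sections 6.7, 6.10 and 8 do not appear, and some text within 6.11 is missing. A worst-value table may exist there. If so, the SAP text should name it and exempt it from the 6.1 rule. Protocol 12.3 provides independent monitoring of targeted safety laboratory data, which protects subjects during the study but does not supply a comparison of doses in the report.

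**Conclusion.** The point holds in a limited form. On the visible text, measured blood-test, vital-sign and ECG values from unscheduled and Early Discontinuation visits reach listings only, and no worst-post-baseline, any-time or ULN-graded summary recovers them. Two related gaps go with it: transaminases and bilirubin are not tabulated jointly although the protocol names potential Hy's law cases, and the handling of an early EoS visit is unspecified.

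The size cannot be stated, because the documents give neither the number of unscheduled draws nor how often they hold a subject's extreme value. The 62%, 42% and 23% figures rest on assumed durations and uniform onset and show only what the schedule can miss. The conclusion assumes that the separate shells and the unseen sections add no such table. The change should be made, but neither the efficacy analysis nor the type I error depends on it.

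**What to change.** Keep the by-visit tables unchanged and make these additions to SAP 6.11.2 to 6.11.4:

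- Worst-post-baseline shift and abnormality tables for each blood analyte, vital sign and ECG interval, using all post-dose values: scheduled, unscheduled, early discontinuation and EoS.
- Separate versions for Part I and after Part I, using the SAP 6.1.1 treatment groups. Re-randomized placebo subjects must not be pooled with subjects on the same dose from the start.
- Peak liver tests by pre-specified multiples of ULN, with a joint table of peak ALT/AST and total bilirubin. No Hy's law screen is defined in the visible text, so the sponsor should set the thresholds in the SAP.
- A rule stating which visit an early EoS assessment is assigned to, and whether it enters the by-visit tables.
- A clause in SAP 6.1 exempting the new tables from the scheduled-only sentence.

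The cost is SAP wording and a few tables from data already collected; visits, sample size and alpha are untouched. The drawback is that subjects with more unscheduled draws have more chances of an extreme value. The retained by-visit tables put that in context. The thresholds and visit rule are best fixed before any unblinded output is produced.
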